9.4	Adherence to the Protocol	77
9.5	Post-study Treatment for Subjects.....	78
9.6	Subject Indemnification.....	78
9.7	Monitoring.....	78
9.8	Storage of Clinical Study Data	78
9.9	Data Safety Monitoring Board and Data Monitoring Committee	79
9.10	Audit and Inspection.....	79
9.11	Confidentiality	79
10	REFERENCES.....	81
11	APPENDIX.....	82

List of Abbreviations and Definition of Terms

ADR	: Adverse Drug Reaction
AE	: Adverse Event
AESI	: Adverse Event of Special Interest
ALT (SGPT)	: Alkaline Transaminase (Serum Glutamic Pyruvic Transaminase)
aPTT	: activated Partial Thromboplastin Time
AST (SGOT)	: Aspartate Transaminase (Serum Glutamic Oxaloacetic Transaminase)
AUC	: Area Under Curve
AUC _(0-inf)	: Area Under the FIX activity time Curve from time zero to infinity
AUC _(0-t)	: Area Under the FIX activity time Curve from zero to a definite time t
BU	: Bethesda Unit
BUN	: Blood Urea Nitrogen
CL	: Total plasma clearance; the volume of blood from which the drug is total removed per unit time
C _{max}	: Observed maximum plasma concentration after administration
CRF	: Case Report Form
DMC	: Drug Monitoring Committee
DSMB	: Data Safety Monitoring Committee
FIX	: Factor IX
rFIX	: Recombinant Factor IX
GMP	: Good Manufacturing Practice
HBV	: Hepatitis B Virus
HCV	: Hepatitis C Virus
HIV	: Human Immunodeficiency Virus
IRB	: Institutional Review Board
IU	: International Unit
IV	: Intravenous
K	: Incremental recovery
KGCP	: Korean Good Clinical Practice
MedDRA	: Medical Dictionary for Regulatory Activities
MRT	: Mean Residence Time
NAb	: Neutralizing Antibody

NOAEL	: No Observed Adverse Effect Level
PD	: Pharmacodynamic
PK	: Pharmacokinetic
PT	: Prothrombin Time
RBC	: Red Blood Cell
SAE	: Serious Adverse Event
SC	: Subcutaneous
SUSAR	: Suspected Unexpected Serious Adverse Reaction
$t_{1/2}$: Terminal phase elimination half-life
TAT	: Thrombin-Antithrombin Complex
T_{max}	: Time to maximum plasma concentration
V_{ss}	: Volume of distribution at steady state
WBC	: White Blood Cell
γ -GT	: Gamma-Glutamyl Transpeptidase

Synopsis

Study title	A Phase 1, Open-label, Multi-center, Dose-escalation Study to Investigate the Safety, Pharmacokinetics and Pharmacodynamics of ISU304 in Previously Treated Hemophilia B Patients
Study centers/ Coordinating investigator	Study Centers: Eulji University Hospital Severance Hospital Pusan National University Hospital Coordinating Investigator: [name], Eulji University Hospital
Study duration	Approximately 24 months after the protocol approval from the institutional review boards (IRBs)
Indication	Previously treated hemophilia B patients
Study objective	To investigate the safety, pharmacokinetics and pharmacodynamics of ISU304 (recombinant factor IX with increased activity) in previously treated hemophilia B patients
Phase and design	Phase 1, open-label, multi-center, dose-escalation
Investigational products	
 Study drug: ISU304 75, 150IU/kg, intravenous or subcutaneous administration Active control: BeneFIX 75 IU/kg, intravenous administration Rescue drug: Treatment currently used by subject to treat hemophilia B
Administration and follow-up period	
 Cohort 1 (n=3): 7 days Single intravenous administration of BeneFIX (75 IU/kg) with 72 hours of observation, followed by single intravenous administration of ISU304 (75 IU/kg) with 72 hours of observation Cohort 2 (n=3): 7 days Single intravenous administration of ISU304 (75 IU/kg) with 72 hours of observation, followed by single subcutaneous administration of ISU304 (75 IU/kg) with 72 hours of observation Cohort 3 (n=3): 9 days Single intravenous administration of ISU304 (75 IU/kg) with 72 hours of observation, followed by single subcutaneous administration of ISU304 (150 IU/kg) with 120 hours of observation Cohort 4 (n=5): 10 days One subcutaneous administration of ISU304 (150 IU/kg) per day for 6 days with 240 hours of observation Cohort 5 (n=minimum 3, maximum 5): 15 days Single intravenous administration of ISU304 (75 IU/kg) is followed by

	subcutaneous ISU304 (150 IU/kg) administration for 9 days with 312 hours of observation
Planned number of subjects	At least 12 subjects
Inclusion criteria	
 1) Previously treated male patients with moderate or severe hemophilia B (documented FIX activity $\leq 2\%$ and exposed to any FIX product for ≥ 150 exposure days (estimated)) 2) Patients must be 12 to 65 years old at the time of screening 3) Patients who have discontinued a previously treated FIX product at least 4 days prior to the administration of investigational product 4) HIV negative, or if HIV positive with a CD4 count $> 200/\mu\text{L}$ (documented < 200 particles/μL or $\leq 400,000$ copies/mL) at the time of screening 5) Voluntary consent to participate in the study
Exclusion criteria	
 1) Patients with a history or a family history of FIX inhibitors 2) Patients with FIX inhibitors (positive result for BeneFIX or ISU304 from inhibitor tests) at the time of screening 3) Patients who have a history of thromboembolic events (myocardial infarction, cerebrovascular disease, venous thrombosis, etc.) 4) Patients with known hypersensitivity, allergy, or anaphylaxis to any FIX product or hamster protein 5) Patients receiving treatment with a FIX product or a bypass agent within 4 half-lives for the agent used (at least 96 hours) prior to the administration of the investigational product 6) Patients who have been exposed to long-term administration (exceeding 14 days) of immunomodulating agents or immunosuppressants such as α-INF or adrenocortical hormones over the past 3 months or who are currently receiving or planning to receive such treatment during the study period 7) Patients who have been administered vaccines during the period of 6 months prior to the administration of the investigational product or plan to receive vaccines during the study period 8) Patients with any other co-existing bleeding disorder (Von Willebrand disease, etc.) 9) Patients with positive D-dimer results ($\geq 0.5 \mu\text{g/mL}$) at the time of screening 10) Patients with platelet counts less than $100,000/\mu\text{L}$ at the time of screening 11) Patients with ALT, AST levels 5 times greater than upper normal limit or total bilirubin, serum creatinine levels 2 times greater than upper normal limit at the time of screening 12) Active hepatitis patients who are HBs Ag positive or anti-HCV Ab positive and require medical treatment at the time of screening

	
13) Patients scheduled for surgery during the study period
 
14) Patients participated in another study within 30 days before screening or scheduled to participate in any other study during the study period

Study timeline/ Data collection	
This study is a phase 1, open-label, multi-center, dose-escalation study to investigate the safety, pharmacokinetics and pharmacodynamics of ISU304 in previously treated hemophilia B patients.
 
All subjects shall give their written consent before participating in this study and only those who meet all of the inclusion criteria and none of the exclusion criteria will be administered the investigational products.
 
This study is comprised of 5 cohorts. Each cohort will receive an identical intravenous administration of 75 IU/kg, with subcutaneous administrations doubling from 75 IU/kg until 150 IU/kg.
 
During the study period, a subject may be hospitalized to facilitate the collection of blood samples for pharmacokinetic (PK)/pharmacodynamic (PD) analysis. Hospitalization itself will not be considered as a serious adverse event if no adverse event occurs. PK/PD analysis and safety assessments will be conducted for each cohort. The Data Safety Monitoring Board (DSMB) and Drug Monitoring Committee (DMC) will be operated after the end of Cohorts 1 to 4. These committees will monitor the PK/PD and safety data from each cohort to determine the continuation of next cohort (Cohorts 2 to 5), target dose, and blood sampling period for PK/PD (including timing of collection). Additional subjects may be enrolled in all cohorts or cohorts may be canceled depending on the results of PK/PD analysis.

Safety endpoints	
 Adverse events after the administration of investigational products (local/systemic/other)¹ Physical examination² Vital signs Electrocardiogram Laboratory tests FIX inhibitors (or neutralizing antibodies) and anti-drug antibodies to investigational products
Pharmacokinetic/ Pharmacodynamic endpoints	
 PK endpoints: observed maximum plasma concentration (C_{max}), terminal phase elimination half-life ($t_{1/2}$), total plasma clearance (CL), volume of distribution at steady state (V_{ss}), area under curve (AUC; $AUC_{(0-t)}$ and $AUC_{(0-inf)}$), mean residence time (MRT), incremental recovery (K), time to maximum plasma concentration (T_{max}) for FIX activity and FIX product PD endpoint: activated partial thromboplastin time (aPTT)
Other endpoints	Demographic data, hemophilia B status, medical history, medication history

¹ Including adverse events of special interest (AESI)

² Includes assessment of tolerability of subcutaneous injection (excluding Cohort 1), local reactions in administration site and systemic reactions after subcutaneous administration of investigational products.

Analysis method	
• Analysis population
- Safety analysis set: All subjects who receive at least one dose of investigational products- PK set: Subjects in the safety analysis set who complete all procedures planned for the cohort and for whom PK samples³ have been obtained at least 4 times after administration.• PK Analysis: Using WinNonlin software (Pharsight, CA, USA)⁴• Bioavailability analysis for subcutaneous administration• Other statistical analysis
- For each cohort, descriptive statistics will be given for each endpoint for each subject using SAS software (SAS Institute Inc, Cary, USA)
------------------------	--

³ The 4 PK sampling points should include at least 2 points within 3 hours after IV administration, or within 12 hours after SC administration. However, Cohort 4 and Cohort 5 subjects can be included in the PK set with samples from 6 hours after the 1st administration and 6 hours after the 6th administration.

⁴ NONMEM software (ICON, MD, USA) will be used for additional analysis, if necessary.

Study Schedules and Procedures

		Screening	1 st /2 nd Hospitali- zation	Administration of investigational product and timing of blood collection for PK/PD analysis ^a										Interim visit /End of a cohort	Post-study safety visit					
Visit no.	1 st administration period			-30 ~ 0	-1 ~ 0	0		1		2		3		4		5				
	2 nd administration period			4 ~ 5	5	6	7	8	9	10	11	3/5(or 6)	+14 (+7)							
Hours after administration		NA	NA	Before administration		0			6	24	48	72	96	120	144	NA	NA			
Informed consent form		X																		
Demographics ^b		X																		
Hemophilia B status ^c		X	X																	
Medical and medication history ^d		X	X																	
Physical examination		X		X				X		X	X	X	X [†]	X	X [†]	X				
Vital signs ^e		X		X				X		X	X	X	X [†]	X	X [†]	X				
Electrocardiogram ^{f,*}		X	X														X			
Inclusion/exclusion criteria		X	X ¹⁾																	
Administration of investigational product					X															
Laboratory tests (central laboratory)^{g,*}																				
Hematology		X	X													X				
Blood chemistry		X	X													X				
Serology		X																		
Urinalysis		X	X													X				
Blood coagulation		X ²⁾	X					X		X	X	X	X [†]	X	X [†]	X				
BeneFIX anti-drug antibody/ neutralizing antibody		X	X ³⁾													X	X			
ISU304 anti-drug antibody/ neutralizing antibody		X	X													X	X			
Bethesda assay			X													X	X			
Safety assessment^h																				
Concomitant medications			X ⁴⁾		X ⁴⁾				X							X				
Adverse events									X ⁵⁾								X			

Study Schedules and Procedures (Cont'd)

		Screening	1 st /2 nd Hospitalization	Administration of investigational product and timing of blood collection for PK/PD analysis ^a										Interim visit /End of a cohort	Post-study safety visit +14 (+7)				
Visit no.	1 st administration period	-30 ~ 0	-1 ~ 0	0				1	2	3	4	5	6						
	2 nd administration period		4 ~ 5	5				6	7	8	9	10	11						
Hours after administration(±min)	Intravenous administration	N/A	N/A	Before administration (-30)	0 (+1) 1 (+3)	0.25 (±3) 2 (±3)	0.5 (±3) 4 (±5)	1 (±3) 6 (±5)	3 (±5) 8 (±5)	6 (±5) 10 (±5)	9 (±5) 12 (±5)	24 (±15)	48 (±120)	72 (±120)	96 (NA)	120 (±180)	144 (NA)	NA	NA
	Subcutaneous administration																		
PK/PD analysis (blood collection) ⁱ																			
Cohort 1	BeneFIX 75 IU/kg w/IV	-	-	X	X	X	X	X	X	X	X	X	X	X	-	-	-		
	ISU304 75 IU/kg w/IV	-	-	X	X	X	X	X	X	X	X	X	X	X	-	-	-		
Cohort 2	ISU304 75 IU/kg w/IV	-	-	X	X	X	X	X	X	X	X	X	X	X	-	-	-		
	ISU304 75 IU/kg w/SC	-	-	X	X	X	X	X	X	X	X	X	X	X	-	-	-		
Cohort 3	ISU304 75 IU/kg w/IV	-	-	X	X	X	X	X	X	X	X	X	X	X	-	-	-		
	ISU304 150 IU/kg w/SC	-	-	X	X	X	X	X	X	X	X	X	X	X	-	-	-		
Cohort 4 ^j	ISU304 150 IU/kg w/SC	-	-	X [‡]	-	-	-	X [‡]	-	-	-	X [‡]	-	-	-	-	-		
Cohort 5 ^k	ISU304 75 IU/kg w/IV	-	-	X	X	-	X	-	-	-	-	-	-	-	-	-	-		
	ISU304 150 IU/kg w/SC	-	-	X [§]	-	-	-	-	-	-	-	X [§]	-	X [§]	-	X [§]	-		
Hospitalization/discharge ^k																			
Hospitalization			X																
Discharge												X							

w/ - with; IV - intravenous administration, SC - subcutaneous administration

^aFor Cohort 4 and Cohort 5, there are no hospitalizations or interim visits, thus replaced by date of 1st administration of the investigational product.[†]- Only for Cohort 4 and Cohort 5[‡]- Blood collection for PK/PD analysis in Cohort 4 take place right before each administration, 6 hours after 1st administration, 6 hours after 6th administration, and 24 hours after 6th

administration.

♀ - Blood collection for PK/PD analysis in Cohort 5 take place before intravenous administration, after administration, 30 min and right before subcutaneous administration, and 24, 72 and 120 hours after 9th subcutaneous administration.

a. Additional visit beyond the designated will be conducted upon request from a subject or subject's representative, or by the investigator's decision. Additional subjects may be enrolled in all cohorts or cohorts may be canceled depending on the results of PK/PD analysis.

b. Gender, date of birth, age, weight, and height

c. Documentation of the lowest FIX activity, year of diagnosis, family history of hemophilia B, history and family history of FIX inhibitors, and previous FIX treatment history

d. Subject's past (within 3 months prior to screening) or current medical history and medication history (within 3 months prior to screening, within 6 months for vaccines)

e. Blood pressure, pulse rate, respiration rate, and body temperature

f. Actual recording date/time, PR, QRS, QT, corrected QT intervals, and investigator's assessment

g. All hematology, blood chemistry, blood coagulation, serology, urinalysis, and Bethesda assay shall be conducted at the central laboratory (SCL; Seoul Clinical Laboratories, KR). Anti-drug antibody/neutralizing antibody tests for BeneFIX and ISU304 shall be conducted at the other central laboratory (HTI, Haematologic TechnoIgiges Inc., USA). However, tests requiring analysis within 24 hours (hematology, urine test) can be conducted at each site. As aPTT is a PD endpoint, it is collected during the PK/PD sampling period. Sample storage and disposal will be carried out according to central laboratory's recommended procedure. For laboratory test conducted for confirmation of inclusion/exclusion criteria, retest is allowed during the screening period as judged by the Investigator.

Hematology: RBC, WBC with differential count (Neutrophil, Lymphocyte, Monocyte, Eosinophil, Basophil), Hemoglobin, Hematocrit, Platelet count, CD4 count (Screening only)

Blood chemistry: Total protein, Albumin, Creatinine, BUN, Uric acid, Total bilirubin, AST (SGOT), ALT (SGPT), γ-GT

Blood coagulation: aPTT, PT international normalized ratio, PT sec, TAT, D-dimer, F1+2, Fibrinogen

Serology: anti-HBV (HBs Ag), anti-HCV (Anti-HCV Ab), anti-HIV (Anti-HIV Ab)

Urinalysis: pH, Protein, Glucose, Urobilinogen, Microscopic exam (if abnormal dipstick test): RBC, WBC

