2.1.3 Expected Adverse Events Related to the Investigational Product

Based on clinical studies and post-marketing experience of the active control (i.e., BeneFIX), the most serious adverse events are systemic hypersensitivity reactions, including bronchospastic reactions and/or hypotension and anaphylaxis, and the development of high-titer inhibitors necessitating alternative treatments to FIX replacement therapy.

In detail, the most common adverse events observed in clinical studies (> 5%) were headaches, dizziness, nausea, injection site reaction, injection site pain, and skin-related hypersensitivity reactions (e.g., rash, hives). Also, the following post-marketing adverse events have been reported: inadequate FIX recovery, inadequate therapeutic response, inhibitor development, anaphylaxis, angioedema, dyspnea, hypotension, and thrombosis.

Considering the findings from previous studies and the mechanism of study drug, it is expected that the study drug will be associated with similar adverse events to the active control.

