5.1.7 Vital Signs

The subject's vital signs (systolic and diastolic blood pressure (mmHg), pulse rate (bpm), respiration rate (bpm), and body temperature (°C)) should be measured and recorded at the time of screening, right before investigational product administration, 6 hours after investigational product administration, all planned visits after administration, interim visits, and end of a cohort (as there is no interim visit for Cohort 4 and Cohort 5, this is replaced by the date of the 1st investigational product administration, and all planned visits after administration is set to 24 hours after each investigational product administration). Blood pressure is measured in a sitting position after resting sufficiently for at least 5 minutes.

If a clinically significant abnormal finding is observed during the examination of vital signs, it should be recorded as current medical history (at the time of screening) or an adverse event (after the administration of investigational products) on the CRF.

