5.1.15 Adverse Events (AEs)

The investigator should collect and review AEs of a subject after administration of the investigational products through interview and/or tests. AEs occurring after the administration of investigational products shall be classified into local, systemic, and other AEs^(10, 13). The adverse events are evaluated using the ruler provided and thermometers at institution for accurate assessment of adverse events.

1) Local AE

All local AEs occurring within 1 hour after the administration of investigational products including pain, tenderness, erythema/redness, urticaria/pruritus, and induration/swelling should be recorded. The severity of the symptoms should also be recorded according to separate AE assessment criteria and the causal relationship with the investigational products should also be evaluated. (Appendix 4. Table – Assessment of Local Adverse Events)

2) Systemic AE

All systemic AEs occurring within 1 hour after the administration of investigational products including fever, fatigue/malaise, chill/pyrexia, , headache, myalgia, arthritis(arthralgia), decreased appetite/loss of appetite, diarrhea, vomiting, constipation, abdominal pain, mucosal skin reaction/rash, vasovagal syncope, dizziness, cough, acute bronchospasm, dyspnea, and hypersensitivity should be recorded according to the AE assessment criteria and the causal relationship with the investigational products should also be evaluated. The severity of the symptoms should also be recorded according to separate AE assessment criteria and the causal relationship with the investigational products should also be evaluated. (Appendix 5. Table – Assessment of Systemic Adverse Events)

3) Other AE

All AEs other than local or systemic AEs occurring after the administration of investigational products should be recorded. The severity of the symptoms should also be recorded according to AE assessment criteria and the causal relationship with the investigational products should also be evaluated.

Adverse events of special interest (AESIs) should be collected and analyzed separately. Following AESIs will be monitored.

- Thrombosis/embolism
- Spontaneous bleeding
- Inhibitor generation/seroconversion
- Anaphylaxis

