9.5 Safety Evaluation

9.5.1 Adverse Events

The summary table for the following AE will be presented by each cohort. In the summary table, the number and proportion of subjects to whom following AE occurred, and its 95% confidence interval and the number of following AEs will be estimated.

- Adverse Event
- Adverse Drug Reaction^a
- Serious Adverse Event
- Serious Adverse Drug Reaction^a
- Early Withdrawal due to AE^b
- Adverse Event of Special Interest^c

^a Adverse Drug Reaction: AE including whose 'Causal Relationship with IP' is assessed "Definitely related", "Probably related", "Possibly related", "Unknown"

^b Early Withdrawal due to AE: AE whose 'Reason for discontinuation' of 'Study Conclusion' is

'Occurrence of an AE that leads treatment discontinuation' and 'Action taken to IP' is "Interrupted"
 c Adverse Event of Special Interest: It is Thrombosis/embolism, Spontaneous bleeding, Inhibitor generation/seroconversion, Anaphylaxis and collected in other AE only

Additionally, the summary table for the following local¹/systemic²/other³ AE will be presented by each cohort. In the summary table, the number and proportion of subjects to whom local/systemic/other AE occurred, and its 95% confidence interval and the number of following AEs will be estimated.

- Adverse Event
- Adverse Drug Reaction
- Serious Adverse Event
- Serious Adverse Drug Reaction
- Early Withdrawal due to AE

¹ Local AE: AEs occurring within 1 hour after the administration of investigational products including pain, tenderness, erythema/redness, urticaria/pruritus, and induration/swelling

² Systemic Adverse Event: AEs occurring within 1 hour after the administration of investigational products including fever, fatigue/malaise, chill/pyrexia, , headache, myalgia, arthritis(arthralgia), decreased appetite/loss of appetite, diarrhea, vomiting, constipation, abdominal pain, mucosal skin reaction/rash, vasovagal syncope, dizziness, cough, acute bronchospasm, dyspnea, and hypersensitivity

³ Other Adverse Event: AEs other than local or systemic AEs occurring after the administration of investigational products

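### No vital signs are scheduled inside the 1-hour window that defines systemic adverse events, and the visit lists for Cohort 5 and Cohort 4 Visit 1 omit the 6-hour set that protocol 5.1.7 requires

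*Combined protocol and SAP*

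**What the plan says.** **Window.** Protocol 5.1.15 defines the systemic category as "All systemic AEs occurring within 1 hour after the administration of investigational products including fever, fatigue/malaise, chill/pyrexia" and further listed events, among them vasovagal syncope, dizziness, dyspnea and hypersensitivity. SAP 9.5.1 uses the same limit: "AEs occurring within 1 hour after the administration of investigational products including fever, fatigue/malaise, chill/pyrexia". Whatever falls outside the local and systemic categories is kept: "All AEs other than local or systemic AEs occurring after the administration of investigational products should be recorded".

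**Measurement.** Note e to the schedule gives the vital-sign set as "Blood pressure, pulse rate, respiration rate, and body temperature". Protocol 5.1.7 times it, after screening, as "right before investigational product administration, 6 hours after investigational product administration, all planned visits after administration, interim visits, and end of a cohort". For Cohorts 4 and 5 the same section redefines the planned post-dose visits as 24 hours after each dose. It does not remove the 6-hour reading.

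**Cover in the first hour.** Note 5 to the schedule and the visit lists in 5.2 require observation for AEs after dosing, with the minimum given as a range from 30 minutes to 1 hour. Protocol 5.1.15 says that AEs are collected by interview or tests, and that a ruler and the site's thermometers are used to assess them. Protocol 5.1.6 has systemic reactions assessed after dosing, with no time.

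**Expected risk.** Protocol 2.1.3 lists, among the most serious events known for the active control, "systemic hypersensitivity reactions, including bronchospastic reactions and/or hypotension and anaphylaxis". It expects a similar profile for the study drug.

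**Analysis.** SAP 9.5.4 tabulates vital signs at the visits where they were collected, and the change from baseline to end of cohort.

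**The concern.** Protocol 5.1.7 treats a clinically significant abnormal vital sign after dosing as an AE, so vital signs are one of the planned routes by which AEs are found. That route is closed for the hour that defines the systemic category. Blood pressure, pulse and respiration are not tied to the observation period at all. Temperature is tied to it only through the general statement about thermometers.

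What is at stake is a transient change that causes no complaint and has resolved by the next reading. Hypotension is the clearest case, because the protocol itself names it as part of an expected serious reaction. The safety board reviews these data before each next cohort (protocol 9.9), and the SAP 9.5.4 tables will hold no planned value from the first hour.

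**Working it through.** The plan gives no figure to reproduce. The check compares scheduled times and counts doses.

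**Step 1: vital-sign timing against the 0 to 1 hour window.**

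| Dosing visits | First post-dose set, 5.1.7 and schedule table | First post-dose set, visit list in 5.2 | Scheduled sets in 0 to 1 h |
|---|---|---|---|
| Cohorts 1 to 3, both doses | 6 h | 6 h | 0 |
| Cohort 4, Visit 1 | 6 h | next visit, about 24 h | 0 |
| Cohort 4, Visits 2 to 6 | 6 h | 6 h | 0 |
| Cohort 5, Visits 1 to 9 | 6 h | next visit, about 24 h | 0 |

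The last column is zero throughout. The second and third columns disagree in two rows. Neither 5.1.7 nor the table exempts those visits.

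**Step 2: how much of the hour is observed.** If observation stops at the lower end of its stated range, 60 − 30 = 30 minutes of the window are unobserved. If it runs to the upper end, none are.

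**Step 3: which doses a change can still reach.** Protocol 1.2.3 describes a change made after Cohorts 1 to 3 had been conducted, and protocol 4.1 says Cohort 5 was included on the results of Cohort 4. The planned doses in Cohorts 1 to 4 are therefore taken as given:

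- Cohorts 1 to 3: 9 subjects × 2 doses = 18
- Cohort 4: 5 subjects × 6 doses = 30
- Total already given: 18 + 30 = 48

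Still reachable is Cohort 5, with 3 to 5 subjects and 9 dosing days each: 3 × 9 = 27 to 5 × 9 = 45 dosing days. Protocol 4.4 also allows added subjects in any cohort.

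**Step 4: Cohort 5 Day 0.** The subcutaneous dose follows the intravenous dose within 30 minutes (± 5). If it comes at 30 minutes, a single reading 30 to 60 minutes after the subcutaneous dose falls 30 + 30 = 60 to 30 + 60 = 90 minutes after the intravenous dose. That is at or beyond the end of the intravenous window, so one reading cannot serve both doses.

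**Step 5: number of readings.** One per dosing day plus one extra per subject on Day 0: 27 + 3 = 30 to 45 + 5 = 50. As a cross-check, each subject has 1 intravenous and 9 subcutaneous doses: 10 × 3 = 30 to 10 × 5 = 50.

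**The case against.** The case against is substantial. The investigator must watch the subject after each dose, AEs are sought by interview or tests, and thermometers are named. A reader might infer that fever or another systemic event in the first hour would be found only if the subject complained. The documents do not support that. For fever, the gap is only that no reading time is set.

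A reader might also infer that systemic events count only in the first hour and are otherwise lost. They are not lost. The limit sorts events into categories; later ones are recorded as other AEs and enter the overall AE table in SAP 9.5.1. Anaphylaxis is an AE of special interest, collected under other AEs and analysed separately, so its capture does not depend on the systemic category.

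Hypotension does not appear by name in the systemic list. That list is open-ended and includes hypersensitivity, and 2.1.3 places hypotension within hypersensitivity, so the link is reasonable but indirect.

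Finally, the AE assessment tables in Appendices 4 and 5 are not in the text available for this review, and a measurement time set there cannot be excluded.

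These points limit the concern but do not remove it. Observation and a thermometer do not detect a blood pressure change without symptoms or visible signs, and the two passages that time vital signs, 5.1.7 and the schedule table, place none in the window.

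**Conclusion.** The point holds as a modest gap in ascertainment. In the hour that defines systemic AEs, a vital-sign change without symptoms can go unrecorded, and temperature has no fixed reading. How many events this would miss cannot be estimated from the documents; the counts above are doses.

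The 6-hour omission in the lists for Cohort 5 Visits 1 to 9 and Cohort 4 Visit 1 is a contradiction with 5.1.7 and the schedule table. A reader might take the roughly 24-hour interval in Cohort 5 as the intended design. The documents do not support that, because the general rule carries no exception.

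A reader might also infer that all doses in the study could still be covered, or that acute vital signs could be compared by product and route. Neither follows: the active control was given only in Cohort 1, and 48 planned doses precede Cohort 5. Nor does any passage present the SAP 9.5.4 tables as evidence of acute tolerability; the risk is that they are read that way unless a limit is stated.

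The conclusion assumes that Cohorts 1 to 4 were dosed as planned before Cohort 5 was added, and that the unseen appendices set no in-window reading.

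**What to change.** 1. For dosing still to come under this version (Cohort 5 and any added subjects), add to the schedule table, 5.1.7 and the dosing-visit lists one recording of the existing vital-sign set within 1 hour after each dose, during the observation already required.
2. On Cohort 5 Day 0, take one set after the intravenous dose and before the subcutaneous dose, and another within 1 hour after the subcutaneous dose. The first then also serves as the pre-dose value for the subcutaneous dose. A change seen in the second still cannot be assigned cleanly to one route.
3. Reconcile the Cohort 5 Visit 1 to 9 lists and the Cohort 4 Visit 1 list with 5.1.7 and the schedule table on the 6-hour set.
4. In SAP 9.5.4, summarise change from that dose's own pre-dose value for the cohort where the reading is collected. State that Cohorts 1 to 4 had no vital signs scheduled in the first hour, so their tables do not describe acute tolerability.

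Cost: about 30 to 50 extra readings by staff already with the subject, and one added time point on the case report form. No extra visit or blood sample is needed.
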